6.2 Clinical Data and Medical History

At every visit medical history will be collected and reviewed from the participant. Medications (especially analgesics including opioids), medical diagnoses, family history, surgical history and other treatments reported will be confirmed via EMR review. At every in-person assessment visit, clinical data will be collected on each participant including weight and height, waist and hip ratio, blood pressure, heart rate, temperature, and pregnancy status (urine pregnancy test if potentially pregnant [premenopausal, ambiguous last menstrual period, intact reproductive system]). Comorbidities will be assessed using the Charlson Comorbidity Index (CCI) and EMR review. If the visit is conducted virtually, clinical data such as blood pressure, will be collected from their most recent in person visit.

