9.4 Duloxetine

All study activities for this arm will take place at the Back & Pain Center, Department of Anesthesiology, at the Burlington Building in Ann Arbor or on a HIPAA compliant virtual platform like Zoom. Participants randomized

Figure 7 Sample MeTime Acupressure App

[figure not shown]

Figure 8 Location of Acupressure Points

to the duloxetine arm will review the dosing schedule for the medication and safety information for the medication at the pre-intervention visit (T2 for Treatment 1 or T3 for Treatment 2) with the study coordinator. At the baseline visits a physical exam was performed by a physician and drug contraindications will be reviewed as an additional precautionary measure.

Participants will then be given 105 pills of 30mg duloxetine with an 8-week dose escalation schedule and an additional 11 pills for those who would like to taper. Participants will be asked to start taking the medication from home, 7 days after the pre-intervention visit (T2/T3 visit). In the event of a shutdown due to COVID, participants may be mailed the study medications by the research pharmacy.

The first day of the medication will be day 1 and subjects will be scheduled for a phone visit with the study team at day 7 and day 42 (or the next business day if this falls on a weekend). A check in call will be made by the study team 48 hours after starting the treatment to address any patient questions or concerns. For days 1-7, patients will take 30mg of duloxetine once a day, in the morning. Starting day 8, participants tolerating the medication will be escalated to 60mg once a day. They will also have the option of staying at 30mg, once a day or stopping the medication (see Figure 9 below).

Participants will be scheduled for a phone visit with the study team at the end of week 1 to discuss dose escalation and at the end of week 6 to discuss dose taper. At the end of the 8-week intervention period, participants will have the option to continue the medication commercially (non-study medication) under the care of their physician or taper off the medication. During the entire 8-week intervention, patients will be asked to keep a daily log of medication dosage, any missed doses, and any side-effects they may have experienced.

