9.4.4 Medication Procurement and Storage

Medications will be procured from the research pharmacy on a weekly basis. Duloxetine will be stored in the research room's double locked cabinet. Temperature in the room must be managed between 20 -25°C (68-77°F); excursions permitted to 15-30°C (59-86°F) – per package insert. A log of maximum/minimum readings will be entered into a log while the drug is in research storage. Medications may also be mailed to patient directly, in the event of a lockdown due to COVID.

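### Duloxetine can be released without a current negative pregnancy test: Protocol 9.4 does not require one, and 6.2 gives no way to do the scheduled test at a fully virtual T2 or T3

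*Protocol*

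**What the plan says.** **Scheduled test.** Protocol 6.6 schedules urine pregnancy testing, where applicable, at T1 to T5; 6.6.3 says T1 to T4. The two differ only on T5, so both cover T2 and T3. The schedules in Protocol 1.3 and SAP Table 1 also carry the test.

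**How it is collected.** Protocol 6.2 says "At every in-person assessment visit, clinical data will be collected on each participant including weight and height", and the same list ends with "temperature, and pregnancy status (urine pregnancy test if potentially pregnant". For other visits it says only: "If the visit is conducted virtually, clinical data such as blood pressure, will be collected from their most recent in person visit".

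**Virtual visits.** Protocol 14 allows T2 to T5 to be virtual or hybrid. Protocol 9.4 lets the duloxetine arm's activities take place "at the Burlington Building in Ann Arbor or on a HIPAA compliant virtual platform like Zoom".

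**Drug release.** Protocol 9.4 says "Participants will then be given 105 pills of 30mg duloxetine with an 8-week dose escalation schedule". On mailing, 9.4 says "In the event of a shutdown due to COVID, participants may be mailed the study medications by the research pharmacy", and 9.4.4 says "Medications may also be mailed to patient directly, in the event of a lockdown due to COVID". Sections 9.4 to 9.4.5 do not mention pregnancy. The duloxetine contraindications in 4.3.1 do not include it.

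**Related safeguards.** Pregnancy is a study exclusion (4.2) and an example of a reason for withdrawal (22.2). Section 19.1 classes duloxetine as category C, with fetal risk not known, and relies on advice plus abstinence or birth control. Section 19.4 requires women of childbearing potential to be tested before MRI and removes those who refuse from the MRI part.

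**The concern.** Two rules are missing around a test that is already planned. First, nothing says how a urine sample is obtained when T2 or T3 is fully virtual. The one sentence on virtual visits points staff to the last in-person visit for clinical data, and pregnancy status sits in the clinical data list without an exception. Second, even where a sample could be taken, no step in 9.4 links the result to the release of drug. The contraindication review that 9.4 does include would not catch pregnancy if staff worked from the 4.3.1 list alone.

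At stake is fetal exposure to a drug whose fetal risk the protocol itself calls unknown, in a participant who should have been excluded or withdrawn. This is a participant-safety point. It has no bearing on the primary endpoint or its analysis.

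**Working it through.** The plan states no figure on this point, so there is none to reproduce. The check sets the rules side by side and then works out how old the last visit test could be.

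**1. The two rules compared**

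| | MRI (19.4) | Duloxetine (9.4, 19.1) |
|---|---|---|
| Urine test required first | Yes | Not stated |
| Consequence of refusal | No MRI | Not stated |
| Other protection | Safety screening form | Safety and contraindication review, contraception advice, phone calls |

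**2. How much drug is released at once**

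Days 1 to 7 take one 30 mg pill a day and days 8 to 56 take two: 7 × 1 + 49 × 2 = 7 + 98 = 105 pills. The initial supply is therefore the whole 8-week course. No later hand-over within the course offers a second chance to test.

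**3. Age of the last visit test at first dose**

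Inputs:
- Visits T1, T2 and T3 at weeks 1, 6 and 15 (Protocol 12.1).
- Delay to first dose of 1 week: "Participants will be asked to start taking the medication from home, 7 days after the pre-intervention visit (T2/T3 visit" (Protocol 9.4).
- Window of ±2 weeks for T2 onwards (SAP 5.6).
- Run-in of 4 weeks (Protocol 3.1), so T2 is no earlier than week 1 + 4 = 5. Two weeks early would be week 4, which breaks the run-in.
- Assumptions: T1 was in person with a test, and the scheduled test was not done at the virtual visit.

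Formula: age = (week of the visit before dosing − week of the last visit test) + 1.

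| Situation | Nominal (weeks) | At the window limit (weeks) |
|---|---|---|
| T2 virtual, last test at T1 | (6 − 1) + 1 = 6 | (8 − 1) + 1 = 8 |
| T3 virtual, last test at T2 | (15 − 6) + 1 = 10 | (17 − 5) + 1 = 13 |
| T2 and T3 both virtual, last test at T1 | (15 − 1) + 1 = 15 | (17 − 1) + 1 = 17 |

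The next scheduled visit test is at T3 for the first course and T4 for the second, in each case after the 8 weeks of dosing.

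**4. Who these figures do not describe**

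Deep-phenotyping participants have their extra visits after T2 and after T3, each before the next treatment (Protocol 10), and 19.4 requires a test before the MRI. The figures counted from T1 also shorten if the baseline back MRI, and its test, took place on a later day, which Protocol 6 allows.

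**The case against.** The strongest reply is that the test is already required. Sections 6.6 and 6.6.3 and both schedules place it at T2 and T3 with no exemption for virtual visits. Protocol 15 says most data collection visits are hybrid, with biospecimens taken at the clinic. Obtaining a sample at an occasional virtual visit could be left to the SOPs, which were not available, nor were the separate data safety monitoring plan and the consent pages. Mailing is described only for a COVID shutdown or lockdown, and 22.1 treats such a shutdown as something that could suspend the study, so new starts by mail may be few. Otherwise drug comes from locked storage in the research room (9.4.4), where an on-site test is possible. Medical history is reviewed at every visit (6.2), safety information and contraindications are reviewed (9.4), and calls follow at 48 hours, day 7 and day 42.

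All of that stands, and it limits the size of the point. It does not close the gap: an on-site test being possible is not the same as being required, and none of the reviews or calls is a test.

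A reader might go further and infer that the protocol tells staff to reuse an old pregnancy result. It does not. The sentence in 6.2 names only blood pressure, and the most that can be said is that it fails to exempt pregnancy status. Nor do the documents support reading this as a duloxetine arm with no pregnancy testing, or as routine mailing of drug to untested participants.

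**Conclusion.** The gap is real and narrow. It applies to a participant who meets the 6.2 description of potentially pregnant, is outside deep phenotyping, and is assigned duloxetine after a fully virtual T2 or T3 at which the scheduled test was missed. It arises chiefly when drug is mailed during a COVID shutdown. For such a participant the last visit test would be about 6, 10 or 15 weeks old at first dose, and up to 8, 13 or 17 weeks at the window limits. These ages assume an in-person T1 with a test and no intervening pre-MRI test. The documents give no basis for counting how many participants this could affect, so no count is offered.

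The priority is minor to moderate, on safety grounds. Confidence is medium, because operating procedures that were not available may already contain such a rule. Even so, a condition on releasing drug belongs in the protocol, where the MRI rule already sits.

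**What to change.** Add to Protocol 9.4: a participant who is potentially pregnant as defined in 6.2 must have a documented negative urine pregnancy test at or after T2 (for Treatment 1) or T3 (for Treatment 2), before duloxetine is dispensed or mailed. If the visit is virtual, the test is done at drug pick-up or with a home kit. A pre-MRI test done in that interval counts.

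Add to Protocol 6.2: pregnancy status is not taken from an earlier visit.

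The cost is two sentences, a few home urine kits, and a possible short delay in drug release while a result is documented. The 7 days already planned between the visit and the first dose leave room for this. No new visit is needed.

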6.3 Physical Exam

The clinical exam will be conducted by study-related physicians or a trained member of the research team and consist of a series of assessments that are routinely used in the care of patients with cLBP. Elements of the physical exam and the pain problem that they are directed to evaluate are described in Section 1.3.

6.4 Physical Function Performance Tests

Three performance tests are included in the baseline phenotyping. The first two performance tests come from the NIH Toolbox measures of motor function, a group of validated assessments that have robust psychometric properties and scoring features⁷¹. The first test is the 2-Minute Walk Endurance Test. This test is adapted from the American Thoracic Society's 6-Minute Walk Test Protocol⁷². Participants walk their usual pace for 2 minutes on a 50-foot (out and back) course while being timed. The participant's raw score is the distance in feet and inches walked in 2 minutes. The test takes approximately 4 minutes to administer. The second test is the 4-Meter Walk Gait Speed Test. This test is adapted from the 4-meter walk test in the Short Physical Performance Battery⁷³. Participants are asked to walk 4 meters at their usual pace. Participants complete one practice and then 2 timed trials. Raw scores are recorded as the time in seconds required to walk 4 meters on each of the two trials, with the better trial used for scoring. This test takes approximately 3 minutes to administer. These tests are particularly appropriate for people with cLBP because walking speed and endurance is affected not only by pain, but also by sedentary behavior and obesity,⁷⁴ which are common in people with cLBP. The final test is the Five Time Sit to Stand Test⁷⁵ which is a valid, reliable measure of physical disability in people with cLBP.^{76,77} In patients with cLBP, the change of position from sit to stand is a good test of how pain affects physical movement and taps a slightly different physical domain than the NIH Toolbox motor assessments. Patients are instructed to stand up 5 times from a chair with their arms folded across their chest as fast as possible while being timed. Inability to rise from a chair five times in less than 13.6 seconds is associated with increased disability.⁷⁵

6.5 Biomechanical Data Collection

Biomechanical data will be collected using the Pheno device during the baseline study visit (T1). Research personnel will be trained on using all study device

[figure not shown]

Figure 3 Harness placement for Low Back

equipment. Additionally, participants will be asked additional screening questions to ensure it is safe to use the Pheno device (see Sections 4.5 and 4.6).

Instructions will ask participants to perform the motions as fast or as far as they can comfortably to avoid above risks. Digital data will be stored in our custom software application on the OSU Amazon Web Services (AWS) server, which is equipped to handle PHI and compliant with 21 CFR Part 11 for electronic records.

6.5.1 Pheno Hardware

Motion assessments performed in Pheno use commercially available IMU sensors (XSens MTw2) that are designed specifically for collecting human kinematics non-invasively. They are powered by very small batteries (similar to those found in commercial activity monitors or smart watches) and do not pose significant electrical discharge risk. Additionally, they are sweat resistant as they are fully sealed except for a small micro-USB charging port.

Though designed for safe human contact, these sensors do not touch our participants in our application as they are mounted on a series of custom harnesses which provide additional insulation. Harnesses will be worn over clothing. Harnesses were designed to be extremely light (a few ounces each), comfortable, and non-intrusive for nearly any body style. All materials are non-abrasive (no exposed velcro, sharp edges, etc.), easy to wipe down with alcohol wipes, non-allergenic (e.g. no latex), and highly flexible. Subjects typically only wear the system for a few minutes at a time so there is minimal risk for long-term discomfort.

6.5.2 Spine Kinematics Data

Kinematic spine data will be captured from the Pheno device mentioned above. Additional kinematic data will be collected from a markered optical motion capture system for a subset of subjects who are able to participate at a location that includes these capabilities. Markered optical motion capture systems use a series of near-infrared cameras to track small reflective markers placed on the harnesses that the participant is already wearing (Figure 4). Though safe for human contact, these reflective markers do not come in contact with the participant in our particular application. Data captured from cameras is non-identifying and primarily includes x-y location of each reflective marker. The inclusion of this additional instrument does not affect subject risk in any way.

Inertial and optical motion tracking systems have been used for several years to quantify biomechanical motion in athletes, patients, and workers and are the standard for safely capturing quality kinematic data in this industry.

Figure 4 Reflective markers (silver dots) that are added to harnesses when using markered optical motion capture system

6.6 Biospecimens

Blood serum, whole blood, urine, and saliva may be collected as part of the global BACPAC phenotyping effort that includes DNA, transcriptomics, proteomics, and other “omic” analyses. Participants will rest quietly for several minutes prior to venipuncture. A maximum of 20ml of blood will be drawn from either arm. Samples will be labeled with coded subject ID numbers. Biospecimens will only be collected at the baseline (T1 visits) for light phenotyping and urine for pregnancy testing, when applicable, will be collected at all 5 time points (T1-T5). All samples will be stored initially at the University of Michigan and may be sent to other MRCs or central biorepositories for future storage or additional analyses. Biospecimen collection for deep phenotyping is described in Section 10.3.

6.6.1 Whole blood

Whole blood will be drawn into PAXgene whole blood RNA tubes (<10mL). The tube is inverted 8-10 times and then stored at room temperature for two hours. Samples are then placed in a -80° C freezer (or -20° C for up to 24 hours) for batch analysis.

6.6.2 Blood Serum

Up to 15mL of blood will be drawn into “red top” containers for the collection of blood serum. Samples are allowed to clot on ice for 15-30 minutes and then centrifuged for 10-20 minutes at 1000-2000rcf for the isolation of serum. Serum is subsequently aliquoted into .5-2mL containers and stored at -80° C for batch analysis of proteins (e.g., proteomics).

6.6.3 Urine

Urine is collected in standard collection cup by the and will only be used for urine pregnancy test at T1-T4.

6.6.4 Saliva

Approximately 2mL of saliva is collected in supplied container (e.g., Oragene, DNA Genotek) and stored at room temperature until transfer to -20 or -80° C for future whole genome sequencing.

6.7 Structural MRI of the Back and Pelvis

Patients will be scanned on a 3T Philips magnet at the main hospital on the Michigan Medicine campus (Department of Radiology, MRI Facility on B2-Level, UH B2B405, [name]). A routine lumbar spine protocol (sagittal T1, sagittal T2 with and without fat saturation, axial T2 in one or two blocks) will be used. This follows the consensus statement from the ACR-ASNR-SCBT-MR-SSR practice parameter guideline for spine scanning. Optional Coronal T1 will be obtained to include sacroiliac joints since SI-joint pain is a confounder in back pain evaluation. A volumetric sagittal T2 will be obtained if time permits, this will allow for broader application between our site and University of California-San Francisco (UCSF). Lastly, if time permits, a routine axial T1 may also be obtained for muscle bulk evaluation. Images will be interpreted by [name], (board certified radiologist with a CAQ in neuroradiology).

Degenerative changes will be scored according to an MRI scoring sheet was developed by UCSF U19 REACH. Scoring of the MRI will include the following; a) BMIC (Bone Marrow Intensity Changes or Modic Changes), b) Endplate defects, c) Disc Quality, d) Facet Joints, e) Stenosis.

6.8 Actigraphy and Ecological Momentary Assessment (EMA)

After completing the screening/baseline activities, participants will receive instruction on the use of the PRO-Diary monitor, which the participant will wear during 5 separate 7-day “home monitoring” periods, at baseline (sent home with watch following baseline visit) and T2-T5 to assess physical activity (objectively measured via accelerometry), and ecological momentary assessment (EMA) of mental and physical symptoms. EMA will be collected during Weeks 1, 6, 15, 24 and 36).

To measure real-time physical activity and collect ecological momentary assessment data, we will utilize the PRO-Diary (Figure 5 <http://www.camntech.com/products/pro-diary/pro-diary-overview>), a wrist-worn accelerometer with a touch-screen user-interface. The PRO-Diary collects physical activity data (via a triaxial MEMS accelerometer) as ‘activity counts’ during regular epochs during the home monitoring period and stores time-stamped self-report data until the participant returns the watch to the lab, where the data will be downloaded for cleaning and analysis.

EMA data will be collected using a wrist-worn PRO-Diary or by distributing surveys via text message through Qualtrics. EMA ratings at wake and bedtime will be initiated by the participant upon waking (not necessarily when they get out of bed) and at bedtime (“lights out” or the time they intend to go to sleep, not necessarily the

Figure 5 Pro-Diary- a wrist accelerometer

time they get into bed). An audible alert (beep) or vibration will alert participants to enter midday ratings; the PRO-Diary will be programmed to deliver the alert at a random time each day between 11:00AM and 3:00PM. The PRO-Diary will display a reminder message to complete bedtime ratings at 8:00PM each day.

6.8.1 Physical activity

The PRO-Diary will collect physical activity data as ‘activity counts’ during regular 15-second epochs at a sampling rate of 50 Hz⁷⁶ during the home monitoring period and store time-stamped self-report data until the participant returns the device back to the lab, where the data can be downloaded for cleaning and analysis. The home monitoring period is 7 days which is recommended to obtain a habitual activity profile and will help control for missing data as literature supports a minimum of 5 days of data needed for valid physical activity measurement in adults.⁷⁷ We will require 10 hours of data/day to be considered valid per recommended guidelines.⁷⁸ Activity counts per minute will be aggregated using custom-set intervals surrounding the EMA ratings. Specifically, these activity counts will be averaged in windows around each EMA rating to provide an estimate of activity that was relatively concurrent with the ratings. This will allow for examination of pain intensity and interference in the context of changes in physical activity. Average activity counts per minute for the entire assessment period will also be calculated to assess overall pre- to post-treatment changes in physical activity. Other physical activity variables that will be generated in aggregate with EMA and over the whole assessment period include: percent time immobile (an index of sedentary behavior) and maximum activity counts (an index of top physical activity intensity).

6.8.2 Sleep Features

Participants will be asked to enter their “to bed” and “wake” times into the PRO-Diary to demarcate wake and sleep time and aid in calculating sleep features. Sleep variables are computed with onboard software, using measurement of nighttime physical activity, assessed in 15 second epochs. Four sleep variables will be examined in this study, which are commonly measured sleep dimensions in studies using accelerometers.⁷⁹ Sleep duration (Total Sleep Time) is the time, in minutes, the individual was asleep. Sleep onset latency (SOL) is the time, in minutes, it takes for an individual to go from a wake state to sleeping. Sleep efficiency (SE) is the percentage of time spent asleep relative to total time spent in bed. Wake after sleep onset (WASO) is the time spent awake in bed after initially falling asleep.

7 PainGuide Run-In Period

After the baseline visit, all participants will be assigned to a web-based behaviorally oriented pain self-management program known as PainGuide (<https://bacpac.painguide.med.umich.edu/>). PainGuide is an online or smartphone accessible website containing education and evidence-based self-management modules for pain. PainGuide offers (a) education about pain, pain mechanisms, types of pain including cLBP, and education about a wide variety of professionally administered pain treatments; (b) a rationale and resources for using a variety of self-management approaches for pain; (c) a system for online monitoring of symptoms and self-management activities; and (d) external resources (e.g., current literature, patient advocacy groups) that can support the use of self-management. Multi-media is used in communicating content including: videos, text, audio files, and embedded apps. PainGuide is based upon FibroGuide, a similar website for Fibromyalgia which already possesses UM IRB approval HUM00124722 PainGuide can currently be accessed on its development server at the following link. Development server: <https://painguide.netlify.app/>

During the baseline visit, participants will be supplied a link for obtaining access to PainGuide. Study staff will help orient the participant to the navigation of the site and will aid with login, password creation, and instruct participants to watch the overview sections on chronic low back pain and the rationale for self-management of pain. Study participants will be encouraged to use this program for a period of four weeks with no specific instructions about how often to visit the site or what to do once there. Participants will continue to have access to PainGuide throughout the trial. Use of the website will be captured passively with website utilization metrics. If study participants lack access to mobile devices or computers, a Kindle device will be lent to them for use during the study.

8 Randomization

Blocked randomization will be used for the randomization schedule. Patients will be assigned to MBSR (n=110), PT and exercise (n=110), acupressure self-management (n=110), or duloxetine (n=110). Participants will be recruited and randomized until all 4 arms of the study have been filled, which will require the recruitment of as many as 500-600 participants given that we anticipate that 10-20% will respond to the PainGuide self-management intervention, withdraw or be lost to follow-up.

